#### 9.4.3 ANALYSIS OF THE SECONDARY ENDPOINT(S)

The primary evaluation will be at the end of the study period (12 to 18-months) using all available data regardless of the period end for participants, and comparisons at 3M will be secondary. For the primary evaluation, we will test the longitudinal effect of a peer mentor led telephone intervention on mentee self-management skills including 1) dialysis adherence (mean number of outpatient dialysis hours per month), 2) mean monthly inter-dialytic weight gain (IDWG), and 3) mean monthly albumin levels. We

will compare the rate of change over time of the monthly secondary endpoints between two intervention groups using linear mixed effects regression model. In the regression model, the secondary endpoint (e.g. monthly mean dialysis hours) is the outcome variable with two main effects (the intervention assignment and months from baseline) and the interaction term between the main effects. The interaction term (i.e. the difference in slopes between two groups) is the primary predictor of interest. There will be three random intercepts to account for mentor effect, facility effect (out of seven facilities) and subject effect (to account for within correlation from repeated measurements). We will evaluate differences in baseline variables identified in Table 6 and if they are different between the groups, we will adjust for them as confounders.

For the secondary evaluation at 3M, we will perform Wilcoxon rank-sum test to compare the 3-months change of secondary endpoints between the intervention mentee and control mentees. To account for confounders, we will also fit linear regression model with two random intercepts. In the regression model, the 3 months-change of secondary endpoint is the outcome variable and the intervention assignment of the mentees is the primary binary predictor. The random intercepts will account for the correlation between mentees who share a common mentor as well as the correlation between mentees who are from a common dialysis facility.

Below, each endpoint is described including its source, scoring and planned analysis approach. Additional details for scoring of surveys is provided in the PEER HD Survey Scoring guide document. Within group (mentors) for change in outcomes over time will also be evaluated.

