## 9.4 STATISTICAL ANALYSES

### 9.4.1 GENERAL APPROACH

Descriptive statistics will be used to provide for each variable: number of observations, mean, standard deviation, median, minimum and maximum for continuous variables; frequencies and proportions for categorical variables. Results will be reported in accordance with the extended CONSORT guidelines for pragmatic clinical trials using two-sided statistical tests and confidences intervals. For all analyses, the overall level of significance will be set at 0.05. All analyses will be adjusted for site. Adjustment variables will be pre-specified in the following sections. All analyses will be performed using SAS v9.4 (SAS Institute, Cary, NC), STATA (College Station, Tx), or R (currently 3.6.1; <https://cran.r-project.org/>).

Analyses of qualitative data will include content analysis, novel code generations as applicable, interpretation and descriptive reporting.

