#### 9.4.2 ANALYSIS OF THE PRIMARY ENDPOINT(S)

##### ED Visit and Hospitalization Count

Each month all enrolled patients will be evaluated for ED visit or hospitalization encounters by both self-report and medical record review. The events will be tabulated each month up to an 18-month period of follow-up. The rates of the composite event will be determined as event per patient-month and compared between the intervention and usual care group using Poisson regression with two random intercepts. In the regression model, the composite counts of ED visits and hospitalization during up to 18-months follow-up is the outcome variable and the intervention assignment of the mentees is the primary binary predictor. The log of follow-up time will be included as offset. The random intercepts will account for the correlation between mentees who share a common mentor as well as the correlation between mentees who are from a common dialysis facility (out of seven facilities). As a randomized controlled trial, we do not anticipate the need for covariate adjustment. However, if evaluation of patient characteristics by group identifies a failure of randomization and imbalance in key characteristics as an example including age, gender, comorbidity, race, or dialysis vintage they will be considered as adjustment variables in the analysis. We will control for type 1 error at 0.05. An exploratory analysis will consider the comparison between the groups but at 3-months of observation after the conclusion of the intervention delivery.

We will perform residual analysis for the mixed effects models. For mixed effects models, we will examine marginal residuals to check linearity and within-subjects covariance matrix and conditional residuals to check outliers as well as normality and homoscedasticity of the residual errors. In case Pearson residual analyses indicate overdispersion in the Poisson mixed effects model, we will perform quasi-Poisson model. We will use robust sandwich estimator in the presence of misspecification of the covariance matrix (i.e. random effects structure).

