#### *Outcomes derived from clinical EHR records*

##### Dialysis treatment schedule adherence (mean minutes missed per month)

This outcome will be summarized as total minutes prescribed per month, minutes delivered per month and the missed minutes is the prescribed minus the delivered minutes. There will be no value less than zero (eg. no accounting for additional minutes).

This is a repeated end-point with values for each month of the observation period (Months 1 through up to 18). The value itself is interval (0 – 240, or higher).

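### The main test of the monthly secondary endpoints is a difference in slopes, but the model has random intercepts only and no firmly specified robust standard error, so its error rate is uncontrolled if patients' trends differ

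*Combined protocol and SAP*

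**What the plan says.** Section 9.4.3 analyses the three record-based secondary endpoints as monthly series in a linear mixed model with arm, month and their interaction. The tested parameter is explicit: "The interaction term (i.e. the difference in slopes between two groups) is the primary predictor of interest". The random part is equally explicit: "There will be three random intercepts to account for mentor effect, facility effect (out of seven facilities) and subject effect". The subject intercept is expected to deal with the repeated measures: "subject effect (to account for within correlation from repeated measurements". The adherence series is described as covering "Months 1 through up to 18". Section 1.2 now limits observation to 12 months for new participants and those not yet at month 12.

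Section 9.4.1 sets the error rate: "For all analyses, the overall level of significance will be set at 0.05", "using two-sided statistical tests and confidences intervals".

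Section 9.4.2, on the primary count endpoint, contains a check and a remedy worded for mixed models. The check is: "For mixed effects models, we will examine marginal residuals to check linearity and within-subjects covariance matrix and conditional residuals to check outliers". The remedy is: "We will use robust sandwich estimator in the presence of misspecification of the covariance matrix (i.e. random effects structure". Neither is repeated in Section 9.4.3.

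**The concern.** A random intercept lets patients differ in level but makes all patients in an arm share one trend. Any real spread in individual trends then goes into the residual. The model treats it as independent monthly noise and averages it over 12 or more records per patient. It is in fact patient-level variation, which only more patients can average out. The standard error of the slope difference is then too small. Positive serial correlation between neighbouring months has the same effect.

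A single common trend is hard to assume here. The entry criteria in Section 5.1 mix patients under 90 days on dialysis with recently hospitalized patients, catheter users and patients with low albumin. Sections 9.4.7 and 9.4.9 plan to examine whether the effect varies with patient characteristics, call minutes and mentor-mentee concordance. Trends may also cluster by mentor, which a mentor intercept cannot capture.

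At stake is the main test of all three endpoints: chance differences in drift could be reported as an effect on self-management or nutrition.

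**Working it through.** **Inputs from the documents.** Two-sided 0.05 (Section 9.4.1); m = 12 monthly values, or up to 18 (Sections 1.2 and 9.4.3); 100 per arm (Section 9.2); about 17 mentors (Section 5).

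**Assumed, because the documents give no value.** Albumin residual SD s = 0.25 g/dL; between-patient slope SD τ = 0 to 0.03 g/dL per month; complete, balanced series.

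**Formulas.**
- Spread of the months: S = m(m² − 1)/12, so S = 143 for m = 12 and 484.5 for m = 18.
- Ratio of slope variance to slope sampling error: R = τ²S/s².
- A patient's fitted slope has true variance (s²/S)(1 + R).
- The intercept-only model uses (s²/S)(1 + R/(m − 1)), because slope deviations take up one of the m − 1 within-patient degrees of freedom.
- True over model-based variance: V = (1 + R)/(1 + R/(m − 1)). The number of patients cancels.
- Actual type I error = 2[1 − Φ(1.96/√V)].

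**The plan's own figure.** With τ = 0, V = 1 and type I error is 5.0%; simulation gave 4.4% to 4.65%. The stated level holds when all patients in an arm share one trend and monthly errors are independent.

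**Worked example, τ = 0.02, m = 12.** R = 0.0004 × 143/0.0625 = 0.915. V = 1.915/1.083 = 1.768. 1.96/√1.768 = 1.474, so type I error is 14.0%.

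| Slope SD (g/dL per month) | m = 12: V | Formula | Simulation | m = 18: V | Formula | Simulation |
|---|---|---|---|---|---|---|
| 0 | 1.00 | 5.0% | about 5% | 1.00 | 5.0% | about 5% |
| 0.01 | 1.20 | 7.4% | 7.7–8.4% | 1.70 | 13.3% | 13.5–14.3% |
| 0.02 | 1.77 | 14.0% | 13.7–14.5% | 3.47 | 29.3% | 28.4–29.7% |
| 0.03 | 2.58 | 22.2% | 21.3–21.9% | 5.66 | 41.0% | 40.5–41.3% |

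The standard error is understated by 1 − 1/√V: from 9% to 38% at 12 months and from 23% to 58% at 18, for slope SDs of 0.01 to 0.03.

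**Other endpoints, on a unit-free scale.** Slope reliability is R/(1 + R). At 12 months, type I error is 6.2% at reliability 0.1, 8.5% at 0.25, 14.8% at 0.5 and 23.7% at 0.7.

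**Serial correlation alone.** With no slope variation and first-order autocorrelation of 0.2 to 0.8 (assumed), type I error is 9.8% to 35.3% at 12 months.

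**With a correction.** Patient-level slopes, or a sandwich clustered on patient, gave 4.4% to 6.1% in simulation. The clustering level matters:
- If 20% of slope variance is shared within mentors, clustering on patient gives about 9% (8.9% and 9.3% in two simulations at 12 months). Clustering on mentor gives 5.9%.
- Clustering on the seven facilities, uncorrected and with a normal critical value, gave about 12% even with no slope variance.

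**The case against.** The strongest objection is that Section 9.4.2 already covers this. Its text speaks of mixed effects models generally, and checking within-subject covariance and residual normality suits the repeated-measures model of Section 9.4.3 better than a single count per patient. An omitted random slope is a misspecified random effects structure, for which the plan commits to a sandwich estimator. A two-step version was simulated, using an F-test for slope variance at 5% as an assumed stand-in for the residual check. It held type I error at 4.7% to 5.6% across slope SDs of 0 to 0.03, with no mentor clustering of slopes. This stands: the safeguard, if carried over and clustered suitably, largely repairs the test.

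It does not settle the matter. The text sits under the primary endpoint, the check has no decision criterion, and no clustering level is named. The standard error would therefore be chosen after the data are seen, and the choices above range from about 5% to about 12%.

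The second objection is that the inflation is assumed. That also stands. At a slope SD of 0.005 and 12 months the error is only 5.6%. A slope SD of 0.03 sustained over 17 monthly steps implies an SD of true albumin change of 0.51 g/dL, which nothing in the documents supports.

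A reader might infer that the plan has a false-positive rate of 8% to 40%. The documents do not support that. They give no slope SD or autocorrelation, and the top of the slope-SD range needs 18 values for every patient, whereas Section 1.2 limits many to 12.

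**Conclusion.** The point holds as a gap in specification. The tested parameter is a slope, the named model has no slope variation between patients, and the remedy elsewhere in the plan is conditional and incomplete.

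Under the albumin assumptions, the model-based test has a type I error of about 5% to 22% with 12 monthly values, and up to about 40% only if all patients had 18. These are illustrations for albumin-like data without serial correlation, not estimates for this trial and not a ceiling: strong serial correlation could do as much or more. Actual follow-up is a mixture of lengths, which the balanced formulas only approximate.

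It would be wrong to infer that the primary result is at risk. The primary analysis models one count per patient with a follow-up offset and tests no slope. Because only secondary endpoints are affected and a workable safeguard is partly in place, this should be fixed but does not threaten the trial's main conclusion.

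**What to change.** Choose one of the following for Section 9.4.3 and state it before the data are analysed.

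1. Give each patient a random intercept and a random slope for month. Keep the mentor and facility intercepts, and add a mentor slope in the intervention arm if it can be estimated from about 17 mentors. State what happens if the model does not converge, keeping the patient slope in every case.
2. Keep the present model but use the sandwich standard error unconditionally for the slope test. Cluster on mentor in the intervention arm and on patient in the control arm, with a small-sample correction.

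The second is simpler if a mentor slope proves inestimable, because a patient slope alone does not cover trends shared within mentors.

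The cost is a sentence or two in the plan and about a line of model code. Intervals will be slightly wider if slopes do not vary; if they do, the extra width is what the data warrant.

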**Table 4. Scientific Questions to be Addressed with the Trial**

Scientific question	Outcome(s)	Analysis
1. Does phone peer support improve outcomes at 18-months (*12 to 18-months)?	
 
Primary: composite endpoint count of ED visit and hospitalization events
 
Secondary: Various as listed above
 
	Poisson regression with two random intercepts. Random intercepts account for clusters by (1) mentor; (2) dialysis unit  See Section 9.4.2 (Primary); 9.4.3 (Secondary)
2. Is a peer mentor training program feasible?	
 
Attendance records
 
Pre- and Post-knowledge test scores
 
Satisfaction with training
 
Summative assessment
 
	Paired t-tests  Descriptive summaries and content analysis of qualitative data
3. Is a peer mentor training program accepted by patient receiving hemodialysis	
 
Satisfaction with intervention
 
Communication rating of mentors
 
	Descriptive  Content analysis of qualitative data

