#### Quality of life

This is measured with the RAND SF-36. Responses are standardized to a 0 to 100 scale and then averaged together to derived 8 subscale scores. Four of these then contribute to the physical component score (PCS), and four contribute to the mental component score (MCS). All values are interval.

For the perception of social support and self-efficacy we will use linear regression with two random intercepts to compare the scores on the PKDSMS, social support survey and quality of life surveys between the intervention mentee and control mentees at the various time points. The outcome variable for the regression is the assessment scores and the predictor of interest is the binary indicator of intervention groups.

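### Two tests are planned for the 3-month secondary comparisons and neither is named as decisive; the rank-sum test omits site and mentor, and can be modestly liberal if mentors differ in effect

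*Combined protocol and SAP*

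**What the plan says.** Section 9.4.3 makes the end-of-study evaluation the main one for the secondary endpoints and states that "comparisons at 3M will be secondary". For month 3 it lists two between-arm analyses of the same quantity, the 3-month change:

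- First, "we will perform Wilcoxon rank-sum test to compare the 3-months change of secondary endpoints between the intervention mentee and control mentees". No stratification, covariate or cluster term is attached.
- Then, "To account for confounders, we will also fit linear regression model with two random intercepts". These intercepts are for mentor and dialysis facility: "The random intercepts will account for the correlation between mentees who share a common mentor", and likewise for patients of a common facility.

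No sentence ranks the two.

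Three other places bear on this:

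- Section 9.4.1 sets two general rules: "All analyses will be adjusted for site", and "For all analyses, the overall level of significance will be set at 0.05".
- Table 4 in Section 9.1 gives the structure for the primary and secondary outcomes: "Random intercepts account for clusters by (1) mentor; (2) dialysis unit". Section 9.4.2 uses the same two intercepts for the primary count.
- The Quality of life entry under 9.4.3 says "we will use linear regression with two random intercepts to compare the scores on the PKDSMS, social support survey and quality of life surveys". It applies this at the various time points and names no rank test.

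**The concern.** The rank-sum test assumes that all observations within an arm are independent. The plan does not believe this of mentees who share a mentor, because it puts a mentor intercept in the primary model, the longitudinal secondary model and the 3-month linear model. The first-named 3-month test is the exception, and no reason is given. As named, it also breaks the plan's own rule on site adjustment.

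The linear model is introduced as a way to deal with confounders, not as the analysis that gives a valid error rate. A reader of the results could therefore meet two p-values for one null hypothesis without knowing which the plan meant to rely on. Month 3 is the end of the intervention, so these results will be looked at. At stake is whether a 3-month difference is declared at the 5% level that Section 9.4.1 sets.

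**Working it through.** **Inputs from the documents.** Two-sided level 0.05 (9.4.1). Individual 1:1 randomization (4.1). 100 patients recruited per group and 73 left after 25% dropout (9.2); 73/0.75 = 97.3, consistent with 100. About 17 mentors (Section 5) or 20 (Section 1.1). Usual-care patients have no mentor, so mentor clusters exist in one arm only.

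**Assumed input.** The mentor ICC of the 3-month change. The documents give none, so values from 0 to 0.20 were used.

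**Formula.** With m mentees per mentor, the design effect in the intervention arm is DE = 1 + (m − 1) × ICC; in the control arm it is 1. The variance of the difference between arms rises by the factor (1 + DE)/2. A test that ignores this has type I error 2 × [1 − Φ(1.96/√((1 + DE)/2))].

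**The plan's own figure first.** At ICC 0, DE = 1 and the formula returns 0.05. Simulated, the rank-sum test gave 0.0512 (73 per arm, 20 mentors) and 0.0490 (100 per arm, 17 mentors). The stated 5% is reproduced when mentors do not differ.

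**Numbers put in, ICC 0.05.**

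- 73 per arm, 20 mentors: m = 3.65, DE = 1 + 2.65 × 0.05 = 1.1325, factor 1.066, 1.96/1.0326 = 1.898, error 0.0577.
- 100 per arm, 17 mentors: m = 5.9, DE = 1 + 4.9 × 0.05 = 1.245, factor 1.1225, 1.96/1.0595 = 1.850, error 0.0643.

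**Simulation.** There were 40,000 trials per setting (standard error about 0.001), with mean effect zero and equal total variance in the two arms. The comparison test uses mentor means against individual controls with Satterthwaite degrees of freedom.

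| ICC | Formula, 73/20 | Rank-sum, 73/20 | Mentor-level, 73/20 | Formula, 100/17 | Rank-sum, 100/17 | Mentor-level, 100/17 |
|---|---|---|---|---|---|---|
| 0 | 0.0500 | 0.0512 | 0.0513 | 0.0500 | 0.0490 | 0.0495 |
| 0.01 | 0.0515 | 0.0502 | 0.0505 | 0.0528 | 0.0534 | 0.0517 |
| 0.02 | 0.0531 | 0.0515 | 0.0480 | 0.0557 | 0.0538 | 0.0490 |
| 0.05 | 0.0577 | 0.0551 | 0.0495 | 0.0643 | 0.0638 | 0.0508 |
| 0.10 | 0.0655 | 0.0648 | 0.0501 | 0.0790 | 0.0771 | 0.0501 |
| 0.20 | 0.0814 | 0.0790 | 0.0487 | 0.1083 | 0.1049 | 0.0498 |

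A smaller run that also covered 73 per arm with 17 mentors and 100 with 20 gave 5.6-6.2% at ICC 0.05 and 6.2-8.0% at 0.10, the same picture within simulation error. The mentor-level test stands in for the planned mixed model, which was not itself simulated here.

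**Site and facility.** With allocation balanced within site and no mentor effect, the rank-sum error was 0.052, 0.046, 0.031 and 0.007 for site differences of 0, 0.5, 1 and 2 SD. Leaving site out therefore makes the test conservative. Facility correlation from 0 to 0.30 under individual randomization gave 0.048-0.052. Mentees who merely resemble each other through matching, with no mentor effect, gave 0.049.

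**The case against.** The strongest reply is that the right analysis is already in the plan. The sentence after the rank-sum test specifies a model with mentor and facility intercepts, the 3-month comparison is expressly subordinate, and if mentoring affects nobody the rank-sum test keeps its level. All of that stands. It limits the size of the point, but it does not settle which test decides or remove the conflict with the site rule.

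Four stronger readings are tempting, and the documents do not support them:

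- *The error rate does exceed 5%.* Patients are individually randomized and mentor clusters form afterwards in one arm. Inflation needs mentors who differ in effect, and no ICC is given. It is a scenario, not a finding.
- *Omitting site is part of the inflation.* The check shows the reverse. The site issue is a contradiction with 9.4.1 and a loss of power.
- *Every 3-month secondary endpoint is affected.* The rank-sum sentence speaks of secondary endpoints in general, but the Quality of life entry assigns the two-intercept regression to self-efficacy, social support and quality of life. The scope is clear only for adherence, interdialytic weight gain and albumin.
- *The error reaches 10% or more at moderate ICCs.* With 100 per arm and only 10 active mentors the simulation gave 7.6% at ICC 0.05 and 10.1% at 0.10. Section 6.1.1 says only that some trained mentors may serve as back-up, and no passage gives 10 as the number who carry the mentees.

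**Conclusion.** The point holds as a gap in specification with a modest, conditional effect on error. Two 3-month tests are planned without a hierarchy, and the first-named one departs from the plan's site rule and from its treatment of mentor correlation. With 73 to 100 patients per arm and 17 to 20 mentors, the rank-sum type I error is 5% at a mentor ICC of 0, about 5-6% at 0.02 or below, 5.5-6.4% at 0.05 and 6.5-8% at 0.10.

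These figures rest on the assumed ICCs, roughly equal numbers of mentees per mentor and a zero average effect. A reader might infer that the trial's conclusions are at risk. They are not: the primary endpoint and the end-of-study evaluation use models with mentor and facility intercepts, and only the supporting 3-month comparisons are touched. The correction is still worth making, because the needed model is already in the same paragraph.

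**What to change.** In Section 9.4.3:

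1. Name the linear model as the single decisive 3-month test: 3-month change on arm, site as a fixed effect, random intercepts for facility and for mentor (mentor applying to mentees only).
2. Preferably state a small-sample t reference such as Satterthwaite or Kenward-Roger, given 17 to 20 mentors and seven facilities.
3. Label the rank-sum result as descriptive, or delete it.
4. Reconcile the general 3-month paragraph with the Quality of life entry, so that each secondary endpoint has one stated 3-month method.

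The cost is wording in the analysis plan, with no new data and no new model. Confidence intervals may be slightly wider where mentor effects vary, while adjusting for site can recover some power.
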